**Title:** Safety and Efficacy of Intrathecal Rituximab in Patients with Lymphoid Malignancies Involving the Central Nervous System

**Primary Investigator:** [name].

**Co-Primary Investigator:** [name].

**Collaborators:** Leukemia Faculty

**Centers:** M. D. Anderson Cancer Center

**Number of Patients:** 25

**Objectives:** to determine the safety and efficacy of intrathecal rituximab in patients with relapsed and/or refractory lymphoid malignancies with involvement of the central nervous system.

#### **Background:**

##### ***Leptomeningeal / Central Nervous System Disease***

Leptomeningeal disease (LMD) or central nervous system (CNS) disease in leukemia occurs when blast cells invade the walls of the leptomeningeal veins over superficial surfaces of the brain. Utilization of prophylactic intrathecal chemotherapy and high-dose systemic chemotherapy reduces the incidence of CNS disease. However, development of CNS disease is still a problem, because if it occurs, the prognosis overall tends to be poor (1, 2).

##### ***Diagnosis***

Diagnosis of CNS leukemia involves assessing the cerebrospinal fluid (CSF) by lumbar puncture (LP) or intraventricular sampling. Signs and symptoms include headache, mental status changes, motor deficits, and seizures. In most patients, the CSF is abnormal (protein concentration greater than 50 mg/dL, leukocyte count greater than 4 per mm^3, and positive cytology). A positive cytology by itself is diagnostic of LMD. In leukemias and lymphomas, the yield of positive cytology following one or two lumbar punctures is approximately 70% (3).

Neuroradiographic imaging can also be involved in the diagnostic workup, to include cranial computed tomography (CT), magnetic resonance imaging (MRI), CT-myelography, and radionuclide CSF flow studies (4). However, imaging studies have a high false negative rate.

##### ***Treatment of Leptomeningeal Disease***

Treatment of LMD involves the entire neuroaxis, therefore treatment must be designed to encompass the entire subarachnoid space. Radiation therapy to the entire neuroaxis produces severe bone marrow suppression and has generally not been effective in controlling active CNS disease even in radiosensitive malignancies (4). Systemic chemotherapy for LMD is limited in its utility due to poor penetration of the blood brain barrier (with the exception of the administration of high dose methotrexate or cytarabine) and due to difficulties attaining prolonged intra-CSF drug exposure. Determining the response to therapy primarily involves the clearance of blasts from the CSF along with clinical improvement.

The incidence of CNS relapse with or without bone marrow recurrence in adults with ALL is approximately 7% (1). In this series, patients were treated with intensive chemotherapy and/or CNS prophylaxis with IT methotrexate and cytarabine. Despite a high response rate (clearing CNS disease), median survival for these patients was 6 months, and the 1-year survival rate was 28%.

In our institution, patients who are diagnosed with CNS leukemia are started on intrathecal chemotherapy on a twice weekly schedule of administration. This continues until two consecutive CSF samples are negative for the presence of blast cells. After the patient's CSF cytology is negative, patients commence on maintenance intrathecal chemotherapy weekly for one month, followed by one intrathecal injection with chemotherapy administration every other week thereafter. Methotrexate has been the most widely employed drug for intrathecal treatment of LMD. The terminal half-life of intrathecal methotrexate is 14 hours. The toxicities of intrathecal methotrexate can be exacerbated by the administration of concurrent systemic chemotherapy or radiation. Cytarabine is another active agent administered intrathecally in the treatment of LMD. Typically, these two agents are given on an alternating schedule to potentially minimize toxicity and maximize effectiveness.

Monoclonal antibody therapy has drastically improved the outlook for several malignancies, including adult acute lymphoblastic leukemia. Recently, Thomas and colleagues reported an increased overall survival in younger patients who received the CD20 specific monoclonal antibody rituximab (5). However, the molecule is large, making it difficult to deliver the agent to the central nervous system. Recently, several reports have been published on intrathecal administration of rituximab. Therefore, we would like to conduct a prospective investigation on the safety and effectiveness of this strategy.

### **Background Drug Information:**

#### ***Systemic Rituximab***

Rituximab is a chimeric monoclonal antibody directed at the CD20 antigen. It was initially approved for systemic use in 1997 to treat non-Hodgkin's lymphoma (6). Subsequent to the drug's approval, it has been studied in a number of different oncologic situations, including chronic lymphocytic leukemia (CLL), acute lymphoblastic leukemia (ALL), and as part of the mobilization program for hematopoietic stem cell transplantation. Recently, the addition of rituximab to chemotherapy has been shown to improve overall survival (OS) in younger patients with CD20 positive ALL (5). Moreover, in CLL, rituximab

combined with fludarabine and cyclophosphamide has also improved the outcome of patients compared to conventional chemotherapy programs (7).

The major toxicities of systemically administered rituximab are primarily related to the infusion of the drug, and may include fever, chills, rigors, rash, headache, and hypotension (6). These reactions are potentially fatal, and are typically seen during the first infusion. Most infusion reactions can be ameliorated by administering the drug slowly, and escalating the infusion rate only as the patient tolerates. Premedications are also vital, and might include histamine blocking agents, acetaminophen, and/or corticosteroids. Other potential toxicities include tumor lysis syndrome and mucocutaneous eruptions. Rarely, reactivation of JC virus leads to progressive multifocal leukoencephalopathy.

Penetration of rituximab across the blood brain barrier is a problem due to the drug's large molecular size. Investigators have conducted pharmacokinetic analyses showing that CSF levels of rituximab are 0.1 – 4% of the concomitant serum concentration (8, 9). Rituximab, while highly effective as a systemic therapy, does not reduce the risk of lymphoma recurrence in the central nervous system (10).

### ***Intrathecal Rituximab***

There is preclinical and clinical experience directly infusing rituximab into the CSF. Rubenstein and colleague have first explored the safety and pharmacokinetics of intraventricular rituximab in four female cynomolgus monkeys (11). The authors noted that high concentrations were able to be achieved, and there was no evidence of neurotoxicity observed. The animals received up to two intraventricular rituximab infusions.

Encouraging animal data led to several instances where intrathecal rituximab was employed in humans. A group from the University of California San Francisco and Memorial Sloan Kettering Cancer Center conducted a phase 1 dose finding study of intraventricular rituximab in patients with recurrent CNS and intraocular lymphoma (12). Patients were to receive 10 mg, 25 mg, or 50 mg for up to nine administrations. Most patients on this study had the drug administered through an Ommaya reservoir. Five out of the six patients initially assigned to the 10 mg and 25 mg cohorts received all nine scheduled rituximab treatments. The dose limiting toxicity in the 50 mg cohort was grade 3 hypertension. These patients also complained of diplopia and chest discomfort that resolved with careful observation and supportive care. Very little toxicity was noted in patients who received 25 mg of intraventricular rituximab. However, one patient in the 10 mg cohort did experience what was defined as white matter changes on MRI raising the possibility of leukoencephalopathy. One patient who received rituximab 25 mg administered via lumbar puncture experienced parasthesias in the sacral distribution that resolved within 10 minutes after drug administration.

The remainder of the experience with intrathecal rituximab has been presented or published in case reports or case series. Most of the reports describe administration of rituximab through an Ommaya reservoir (13). Only one case series to date (to our knowledge) describe the use of intrathecal rituximab in patients with B-cell ALL (14). A group from Mexico tested the efficacy of intrathecal rituximab in the

setting of CNS leukemia refractory to conventional intrathecal therapy (combination of methotrexate, cytarabine, and corticosteroids) (Jaime-Perez). Before the rituximab, these patients had undergone a median of 23 intrathecal lumbar punctures with administration of chemotherapy and steroids. These patients received rituximab 10 mg diluted in 6 mL of saline solution intrathecally weekly for 4 weeks. After the fourth dose, all 7 patients' CSF samples were negative for leukemia cells. No neurotoxicity was observed. After 24 months of follow up, 5 of the 7 patients remained without CNS involvement of the leukemia.

### **Inclusion Criteria**

Patients must have relapsed or refractory CD20+ lymphoid malignancies with either documented CNS involvement or peripheral nerve infiltration.

Patients 3 years of age and older are eligible after 3 patients (age 15 or older) have been treated and did not experience a dose limiting toxicity. Patient 3 to 15 years of age will follow the dose escalation schema independent of the adults.

ECOG performance status measure will be used. (ECOG Performance Status less than or equal to 3)

Adequate liver function (bilirubin less than or equal to 3 mg/dL within 24 hours of enrollment)

Adequate renal function (serum creatinine less than or equal to 3 mg/dL within 24 hours of enrollment)

Urine pregnancy test for women of childbearing potential (defined as *not* post-menopausal for 12 consecutive months or no previous surgical sterilizations). A negative urine pregnancy test is required within 48 hours of initiating study drug.

Signed informed consent

### **Exclusion Criteria**

Known active meningeal infection

History of severe infusion reaction to any monoclonal antibody

### **Treatment Plan**

Rituximab will be administered via lumbar puncture at a dose of 10 – 25 mg according to the dose escalation procedures outlined below.

Standard premedications for each lumbar puncture will be administered (benzodiazepine for anxiolysis as well as a topical anesthetic)

Additional premedication will be administered to prevent infusion related complications. 30 minutes prior to each lumbar puncture, patients should receive diphenhydramine (12.5 – 50 mg IV), famotidine (20 – 40 mg IV, and acetaminophen 650 mg PO). Patients may also receive corticosteroid as a premedication at the discretion of the Attending Physician. If in the best interest of the patient, as judged by the Attending Physician, any of the above premedications can be omitted with documentation of the reason why a particular medication was not to be prescribed.

After each intralumbar administration, the patient will be instructed to lie flat for one to two hours, and longer if possible

Rituximab is commercially available, patient and/or insurance provider will be responsible for the cost of the drug. Rituximab will be commercially supplied as a 10 mg/mL solution

Drug Preparation: the 10 mg dose of rituximab will be diluted to a total volume of 5 mL with preservative free 0.9% sodium chloride. The 25 mg dose of rituximab will be diluted to a total volume of 6.3 mL with preservative free 0.9% sodium chloride.

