#### Selection of Patients:

Patients will be eligible for the study if they relapsed and/or refractory CD20+ lymphoid malignancies (all patients beyond complete remission 1 are considered eligible). Upon suspicion of LMD, the patients will be screened for the protocol. The preference at this point will be for the patient to receive a diagnostic lumbar puncture (i.e., no chemotherapy administered). However, if it is deemed necessary to instill conventional chemotherapy (e.g., methotrexate or cytarabine) during the first lumbar puncture, these patients will still be eligible for the protocol. The two groups will be analyzed separately for all outcomes (i.e., patients who received no intrathecal chemotherapy prior to receiving intrathecal rituximab, and patients who received cytarabine or methotrexate before commencing intrathecal rituximab). If a patient had received IT methotrexate or cytarabine and is subsequently enrolled, at least 48 hours should elapse from the administration of methotrexate or cytarabine to the first application of IT rituximab.

Once enrolled, the patients will go on to receive rituximab 10 mg intrathecally twice weekly until 2 consecutive CSF samples are negative for the presence of blast cells 48 hours must elapse between intrathecal rituximab doses. Thereafter, rituximab 10 mg intrathecally will be administered weekly for an additional 4 weeks, followed by intrathecal rituximab 10 mg administered once every other week for an additional 8 weeks.

After the first three patients are enrolled and followed for at least 2 weeks, if no dose limiting toxicity is experienced, all subsequent patients will be given rituximab 25 mg intrathecally on an identical schedule as described above. This dose was identified as the maximum tolerated dose in the phase I study

conducted by Rubenstein and colleagues. If excessive toxicity is noted in the first 3 patients given rituximab 25 mg (with at least two weeks of follow up), we will move back to the 10 mg dose, and that will be the final dose employed going forward.

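### Children are eligible from age 3, but the acetaminophen premedication is one fixed 650 mg dose with no age or weight term and no stated reduced dose

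*Protocol*

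**What the plan says.** Protocol, Inclusion Criteria: "Patients 3 years of age and older are eligible after 3 patients (age 15 or older) have been treated", provided that none of those three had a dose-limiting toxicity. The same paragraph adds: "Patient 3 to 15 years of age will follow the dose escalation schema independent of the adults". These two provisions concern the rituximab dose.

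Protocol, Treatment Plan: "30 minutes prior to each lumbar puncture, patients should receive" three drugs, namely "diphenhydramine (12.5 – 50 mg IV"), "famotidine (20 – 40 mg IV" and "acetaminophen 650 mg PO". The sentence covers patients as a whole, with no age group singled out. Diphenhydramine has a 4-fold range, famotidine a 2-fold range and acetaminophen a single figure. The Attending Physician may depart from the list in one stated way: "any of the above premedications can be omitted with documentation of the reason why a particular medication was not to be prescribed".

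No other section of the protocol gives a paediatric or weight-based premedication dose. The SAP text covers statistical considerations only and does not mention premedication. Weight is recorded under Pre-Treatment Evaluation and again under During Treatment Evaluation, but no dose is tied to it.

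**The concern.** The protocol treats children separately for the study drug: they wait for three older patients and then have their own escalation. That separation does not extend to the supportive drugs given with each dose. A 3-year-old and a 70 kg adult have the same written acetaminophen dose.

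The stake is the size of each single dose in a small child. Omission, the one written alternative, also has a cost. The Treatment Plan gives these drugs to prevent infusion-related complications, and the background section on systemic rituximab treats premedication as essential and infusion reactions as potentially fatal. A child whose physician thinks 650 mg too much therefore has no stated reduced dose to fall back on.

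**Working it through.** The plan reports no figure to reproduce here. The check is a text comparison followed by dose divided by weight.

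**Inputs from the protocol.** Minimum age 3 years (Inclusion Criteria). Acetaminophen 650 mg, famotidine 20 to 40 mg, diphenhydramine 12.5 to 50 mg (Treatment Plan).

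**Assumed inputs.** The documents give no body weights. I take 14 kg for the youngest eligible children and 25 kg for an older child, and compare with adults of 45 kg and 70 kg so that the result does not depend on one adult weight.

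**Acetaminophen, 650 mg / weight.**

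| Weight | mg/kg | Ratio to 70 kg adult | Ratio to 45 kg adult |
|---|---|---|---|
| 14 kg | 650/14 = 46.4 | 70/14 = 5.0 | 45/14 = 3.2 |
| 25 kg | 650/25 = 26.0 | 70/25 = 2.8 | 45/25 = 1.8 |
| 45 kg | 650/45 = 14.4 | | |
| 70 kg | 650/70 = 9.3 | | |

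Varying the youngest weight from 12 to 18 kg gives 650/12 = 54.2 down to 650/18 = 36.1 mg/kg. That is 70/12 = 5.8 down to 70/18 = 3.9 times the 70 kg adult, or 45/12 = 3.8 down to 45/18 = 2.5 times the 45 kg adult. The direction holds throughout.

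**Famotidine.** Here the lowest listed child dose is set against the highest listed adult dose, the comparison kindest to the protocol.

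- Floor: 20/14 = 1.43 mg/kg and 20/25 = 0.80 mg/kg.
- Adult maximum: 40/70 = 0.57 mg/kg, or 40/45 = 0.89 mg/kg.
- At 14 kg the floor is 1.43/0.57 = 2.5 or 1.43/0.89 = 1.6 times the adult maximum.
- At 25 kg it is 0.80/0.57 = 1.4 times against the 70 kg adult, but 0.80/0.89 = 0.9 times against the 45 kg adult, so the excess disappears.
- The floor exceeds the adult maximum only below 20 × 70/40 = 35 kg (70 kg adult) or 20 × 45/40 = 22.5 kg (45 kg adult).

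**Diphenhydramine.** On the same comparison the floor exceeds the adult maximum only below 12.5 × 70/50 = 17.5 kg (70 kg adult) or 12.5 × 45/50 = 11.25 kg (45 kg adult). Its range absorbs most of the size difference, so it is not part of the problem.

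**The case against.** The strongest reply is that the protocol compels nobody to give a small child 650 mg. The wording is that patients should receive the drugs, the physician already judges each drug for each patient, and nothing forbids a smaller dose. This stands. A reader might infer that the text leaves only 650 mg or nothing; the documents do not support that. The gap is silence about a reduced dose, next to a fixed figure that is the default for an eligible 3-year-old.

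A second reply is that a high mg/kg figure does not show an excessive dose. This also stands. The documents contain no paediatric acetaminophen or famotidine limit, so the finding is a multiple of the adult amount and nothing more. Those multiples rest on assumed weights and on per-kilogram comparison.

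Three further extensions are tempting and fail:

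- *The blood-pressure rule has the same defect.* Supportive Care gives a fixed labetalol dose and thresholds without regard to age, but the rule applies only when triggered, and that section expressly lets the treating physician tailor it. No change is needed there.
- *The exposure can be counted over the schedule.* After the twice-weekly phase, dosing is "weekly for an additional 4 weeks, followed by intrathecal rituximab 10 mg administered once every other week for an additional 8 weeks", but the twice-weekly phase runs until two consecutive negative samples and has no fixed length. A firm puncture total does not follow, and no accumulation between doses is claimed.
- *Famotidine is as serious as acetaminophen.* It is not: at 25 kg the excess depends wholly on the adult weight chosen.

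Finally, few children may enrol. The documents do not say how many are expected, entry is conditional, and the trial is capped at 25 patients. That limits how often the problem could arise but does not make the written dose suitable for an eligible child.

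**Conclusion.** The point holds for acetaminophen in small children. The single stated dose for everyone aged 3 and over gives, at assumed weights of 14 and 25 kg, 46 and 26 mg/kg: 3.2 to 5.0 times and 1.8 to 2.8 times the per-kilogram amount of a 45 to 70 kg adult. The famotidine floor is a lesser instance, confined to children below roughly 22.5 to 35 kg.

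This is a cheap improvement for patient safety. It is not a flaw in the statistical design: the primary endpoint, the sample size and the efficacy and toxicity stopping rules are untouched.

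**What to change.** Make two edits to the premedication paragraph of the Treatment Plan.

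1. Add: *The amounts above apply to patients aged 15 or older. Patients under 15, and older patients below the weight at which institutional standards use adult doses, receive weight-based premedication under institutional paediatric standards, not exceeding the amounts above.*
2. In the sentence that allows departures, replace *omitted* with *omitted or dose-reduced for age or weight*, keeping the requirement to document the reason.

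The wording under 15 is deliberate, because the Inclusion Criteria place age 15 in both the older and the younger group.

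The cost is one short amendment. Weight is already recorded before and during treatment, so no new procedure or data item is needed, and eligibility and monitoring stay as they are. Supportive Care needs no change.

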#### Selection of Patients:

Patients will be eligible for the study if they relapsed and/or refractory CD20+ lymphoid malignancies (all patients beyond complete remission 1 are considered eligible). Upon suspicion of LMD, the patients will be screened for the protocol. The preference at this point will be for the patient to receive a diagnostic lumbar puncture (i.e., no chemotherapy administered). However, if it is deemed necessary to instill conventional chemotherapy (e.g., methotrexate or cytarabine) during the first lumbar puncture, these patients will still be eligible for the protocol. The two groups will be analyzed separately for all outcomes (i.e., patients who received no intrathecal chemotherapy prior to receiving intrathecal rituximab, and patients who received cytarabine or methotrexate before commencing intrathecal rituximab). If a patient had received IT methotrexate or cytarabine and is subsequently enrolled, at least 48 hours should elapse from the administration of methotrexate or cytarabine to the first application of IT rituximab.

Once enrolled, the patients will go on to receive rituximab 10 mg intrathecally twice weekly until 2 consecutive CSF samples are negative for the presence of blast cells 48 hours must elapse between intrathecal rituximab doses. Thereafter, rituximab 10 mg intrathecally will be administered weekly for an additional 4 weeks, followed by intrathecal rituximab 10 mg administered once every other week for an additional 8 weeks.

After the first three patients are enrolled and followed for at least 2 weeks, if no dose limiting toxicity is experienced, all subsequent patients will be given rituximab 25 mg intrathecally on an identical schedule as described above. This dose was identified as the maximum tolerated dose in the phase I study

conducted by Rubenstein and colleagues. If excessive toxicity is noted in the first 3 patients given rituximab 25 mg (with at least two weeks of follow up), we will move back to the 10 mg dose, and that will be the final dose employed going forward.

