### **Statistical Considerations**

The primary outcome of the study will be response rate. Time to recurrence of CNS leukemia and overall survival will be secondary outcomes. Time to recurrence and survival will be considered from the date of CNS relapse diagnosis.

There is no well-defined metric to measure response to treatment in patients with peripheral nerve involvement only. Clinical and radiologic response will be recorded and it is expected that few to no patients with only peripheral nerve involvement will actually be involved and therefore the statistical analysis will not be affected.

A maximum of 25 patients will be enrolled in this phase I/II study, with about 12 patients/year.

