### **Phase I**

First, phase I study is performed to assess the safety of two dose levels for rituximab: 10mg and 25mg. These two dose levels have been previously in a small series (12). A 3+3 design will be used to for dose escalation. Detailed dose escalation rules are described in the following section. A maximum of 12 patients will enroll in the phase I study.

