### **Dose Escalation Procedures**

The dose of treatment agent will be escalated in successive cohorts of patients. The starting dose is at dose 0 as shown in table 1. Enroll 3 patients at the dose level and proceed to the next higher dose level with a cohort of 3 patients until at least 1 patient experiences a dose-limiting toxicity (DLT).

DLT is defined as a clinically significant adverse event or abnormal laboratory value assessed as unrelated to disease progression, intercurrent illness, or concomitant medications and meeting the NCI common terminology criteria that are CTCAE Grade 3 or 4.

An adverse event must be clinically significant to define DLT e.g. alopecia, study drug-related fever, electrolyte abnormalities (including K, Na, Cl, HCO3, Mg, Ca) that are < Grade 3 will not define the DLT. Drug-related Grade 3-4 nausea and vomiting not controlled with adequate therapy will be considered DLTs.

If only 1 of 3 patients experiences a DLT at a given dose level, enter 3 additional patients at the current dose level. If only 1 of 6 patients experiences a DLT at a given dose level, proceed to the next higher dose level with a cohort of 3 patients. If at least 2 of 3 or 2 of up to 6 patients experience a DLT at a

given dose level, then the MTD has been exceeded (stopping dose). Once the MTD has been exceeded, treat another 3 patients at the previous dose level if there were only 3 patients treated at that dose level. The MTD is defined as the highest dose level in which 6 patients were treated with at most 1 experiencing a DLT during the 1st cycle.

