In summary, our dose escalation plan is as follows: during phase I, the starting dose is 10 mg and dose escalation will follow a 3 + 3 design. After three patients have received 10 mg, if there is no DLT, the next cohort of three patients will receive 25 mg. If there is one DLT in the initial three patients, an additional three patients will be treated at 10 mg. If 2/6 patients experience a DLT at 10 mg, the study will be closed. If less than or equal to 1/6 at 10 mg experience a DLT, we will enroll the next three patients at 25 mg. The maximum dose on this protocol is 25 mg, thus, no further dose escalation will occur. If 1/3 patients at 25 mg experience a DLT, we will enroll three additional patients at 25 mg. If 2/6 experience a DLT, all subsequent patients will receive 10 mg, and that will be the final dose. If less than or equal to 1/6 experience a DLT at 25 mg, the remainder of the patients enrolled will receive 25 mg. If 2/3 or 2/6 patients experience a DLT at the 10 mg dose, the study will be terminated.

Table 1. Dose levels of rituximab

| Dose level        | rituximab |
|-------------------|-----------|
| 0 (starting dose) | 10 mg     |
| 1                 | 25 mg     |

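### Children appear to have their own escalation from 10 mg, but the dosing text moves every later patient to 25 mg with no age exception, and the phase I maximum of 12 is sized for one track

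*Protocol*

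**What the plan says.** **Entry and escalation for children.** Under Inclusion Criteria, patients from age 3 become "eligible after 3 patients (age 15 or older) have been treated and did not experience a dose limiting toxicity". The next sentence reads: "Patient 3 to 15 years of age will follow the dose escalation schema independent of the adults". No dose is given there.

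**Where the dose comes from.** Treatment Plan sets a range of 10 to 25 mg, to be given "according to the dose escalation procedures outlined below". The summary under Dose Escalation Procedures says that "the starting dose is 10 mg and dose escalation will follow a 3 + 3 design", and Table 1 lists 10 mg as dose level 0.

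**The move to 25 mg.** Selection of Patients says that after three patients have been enrolled and followed for at least two weeks without a DLT, "all subsequent patients will be given rituximab 25 mg intrathecally on an identical schedule as described above". The summary under Dose Escalation Procedures likewise assigns 25 mg to everyone still to be enrolled once that dose is cleared. Neither place mentions age.

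**Sizes.** Statistical Considerations: "A maximum of 25 patients will be enrolled in this phase I/II study". Phase I, in the protocol and again in the SAP: "A maximum of 12 patients will enroll in the phase I study". Dose Escalation Procedures: "The MTD is defined as the highest dose level in which 6 patients were treated with at most 1 experiencing a DLT". Phase II allows up to 22 patients in a single arm at one recommended dose. The statistical sections of the protocol and the SAP mention no paediatric track.

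**The concern.** The event that opens the study to children is nearly the event that moves the study to 25 mg. Both are three patients without a DLT; Selection of Patients adds two weeks of follow-up. So the two rules collide when the first child becomes eligible, or about two weeks later. Staff dosing from Selection of Patients would give that child 25 mg. Staff applying the paediatric rule would give 10 mg. The mistake cannot be undone once the intrathecal dose is given.

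The statistical sections also describe a single escalation, with one phase I maximum, one MTD, one group of six patients at the MTD and one phase II dose. They do not say whether two paediatric DLTs at 10 mg would end the whole study, or what phase II does if the two age groups end with different MTDs. A 15-year-old falls in both age groups.

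**Working it through.** **1. The dosing texts side by side, for the first child after three adults without a DLT**

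| Place in the protocol | Dose for that child |
|---|---|
| Inclusion Criteria, with Dose Escalation Procedures and Table 1 | 10 mg (start of a separate track) |
| Selection of Patients, read literally | 25 mg |

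Ratio: 25 / 10 = 2.5. The children affected are the first three, or six if the paediatric 10 mg level expands. The documents do not say how many children are expected.

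**2. Reproducing the plan's own sizes**

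- Phase I, one track: 2 dose levels x 6 patients = 12. The plan says 12.
- Phase II ceiling, one track: 25 - 3 patients at 10 mg = 22. The plan says 22.

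Both figures match a single track exactly.

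**3. Two tracks**

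Maximum: 2 tracks x 2 levels x 6 = 24.

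The detailed rules under Dose Escalation Procedures require six patients at the MTD, and a step back to fill 10 mg to six if 25 mg fails. The paths of one track that reach an MTD decision are then (10 mg + 25 mg, plus any return to 10 mg):

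- 3+6 = 9; 6+3 = 9; 3+3+3 = 9
- 6+6 = 12; 3+6+3 = 12

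Two such tracks need 9+9 = 18, 9+12 = 21 or 12+12 = 24. Under a shared maximum of 12, an adult track of 9 or 12 leaves 3 or 0 places for children.

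The summary in the same section expands 25 mg only after one DLT in three. If 0/3 at 25 mg is accepted without expansion and the step back is kept, a track with no DLT uses 3+3 = 6. Two tracks then fit in 12 only if none of the four cohorts of three has a DLT. If the step back is dropped as well, a track that fails at 25 mg in its first three patients also ends at six.

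**4. How likely two tracks are to exceed 12**

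The documents give no DLT rates, so these are assumptions. The same rates apply to both tracks, and early closure at 10 mg is included.

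| DLT rate at 10 / 25 mg | Six required at MTD | 0/3 at 25 mg accepted, step back kept |
|---|---|---|
| 5% / 10% | 99% | 57% |
| 10% / 20% | 96% | 76% |
| 20% / 30% | 83% | 72% |

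**5. Effect on phase II at 25 mg, the first three adults having cleared 10 mg**

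- No child treated at 10 mg: 25 - 3 = 22
- Three children at 10 mg, both groups escalate: 25 - 3 - 3 = 19
- Paediatric 10 mg level expands to six: 25 - 3 - 6 = 16

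Table 3 was recomputed by exact binomial recursion from the printed posterior rule, with looks from patient 6 to patient N-1. Early stopping probability at true toxicity 0.2 / 0.3 / 0.4 / 0.5:

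| N | Result |
|---|---|
| 22 (printed) | 0.05 / 0.22 / 0.54 / 0.82 |
| 22 (recomputed) | 0.050 / 0.228 / 0.539 / 0.824 |
| 19 | 0.048 / 0.209 / 0.491 / 0.773 |
| 16 | 0.046 / 0.191 / 0.442 / 0.712 |

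The futility rule of 0/9 acts at the ninth patient, so it does not change at these sizes.

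**The case against.** The best defence is that the paediatric start is already clear enough. Only Inclusion Criteria addresses children's escalation, and Treatment Plan refers the dose to the escalation procedures, which begin at 10 mg. A literal reading of Selection of Patients would leave the separate paediatric escalation with nothing to do. That section is also an abridgement: it omits the expansion after one DLT in three, so it is not exact for adults either. This stands as to intent, and 10 mg is the most likely reading. It does not remove the gap, because no text gives the paediatric rule priority and the 25 mg sentence sits where the dose and schedule are set out.

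A reader might infer that every two-track path exceeds 12. The documents do not support that, since the escalation summary can be read to end a track at six patients.

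A reader might also infer that enrolling children makes the phase II figure of 22 wrong. It does not. The figure is a ceiling, and 19 can arise with no child enrolled: one DLT among the first three adults expands 10 mg to six, and 25 - 6 = 19.

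Finally, patients at the MTD count toward phase II, so expanding that cohort to six gives the same dose under another label, and even 24 fits within the total of 25. That limits the practical harm of the number 12, but 12 is still wrong for two tracks. The SAP extract repeats the protocol text and is not independent evidence.

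**Conclusion.** The point holds as a conflict in the current text, not as proof that children were meant to start at 25 mg. The probable intent is 10 mg; the literal dosing text gives 25 mg, 2.5 times as much, to the first children on adult data alone.

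The phase I maximum of 12 is right for one track. Two tracks can need up to 24. They need 18 to 24 if both reach an MTD decision with six required at the MTD. With the step-back rule kept, 12 is enough for both only if no DLT occurs in any of four cohorts of three and 25 mg is accepted without expansion.

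The probabilities in the working rest on assumed DLT rates. The conflict and the counts do not. Because the unclear rule sets a child's intrathecal dose and the correction is short, it should be made before any child is enrolled.

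**What to change.** 1. **Selection of Patients:** replace the escalation sentences with a reference to Dose Escalation Procedures.
2. **Dose Escalation Procedures, protocol and SAP:** state that the 3+3 rules apply separately to patients aged 15 or older and to patients aged 3 to under 15, each group starting at 10 mg. Word the summary's assignment of remaining patients to 25 mg by age group, and use the same age boundary under Inclusion Criteria.
3. **Phase I, protocol and SAP:** restate the maximum as 12 per age group (up to 24), within the study total of 25.
4. **Two rules for the sponsor to choose and write down:** whether paediatric DLTs at 10 mg close the whole study or only that age group, and how phase II proceeds if the two MTDs differ. Phase II is specified as one arm at one dose, so 10 mg and 25 mg patients should not be pooled under one response prior and one toxicity boundary without justification.

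**Cost.** A text amendment; the total stays at 25. If children are treated at 10 mg before escalating, fewer patients reach the phase II dose. With 19 instead of 22, the Table 3 stopping probability at 40% toxicity falls from 0.54 to 0.49. The approximate 95% half-width at a 25% response rate, 1.96 x sqrt(0.25 x 0.75 / n), widens from 18.1 to 19.5 percentage points. The existing ceiling of 22 already permits this; adding Table 3 rows for the smaller sizes would make it visible.
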